4.8. Table shell for presenting the primary analysis results

MO and Surgery Combined						
	Number of Observed Events (%)		Odds Ratio		Absolute Difference	
Outcomes	Intervention (#patients=XX) (#episodes = XX)	Control (#patients=XX) (#episodes = XX)	Estimate (0.95 CI)	p-value	Estimate (0.95 CI)	p-value
EDTR Day 30	XX (XX%)	XX (XX%)	X.XX (X.XX to X.XX)	X.XXX	X.XX (X.XX to X.XX)	X.XXX
EDTR Day 90	XX (XX%)	XX (XX%)	X.XX (X.XX to X.XX)	X.XXX	X.XX (X.XX to X.XX)	X.XXX
Admission Day 30	XX (XX%)	XX (XX%)	X.XX (X.XX to X.XX)	X.XXX	X.XX (X.XX to X.XX)	X.XXX
Admission Day 90	XX (XX%)	XX (XX%)	X.XX (X.XX to X.XX)	X.XXX	X.XX (X.XX to X.XX)	X.XXX
MO Only						
	Number of Observed Events (%)		Odds Ratio		Absolute Difference	
Outcomes	Intervention (#patients=XX) (#episodes = XX)	Control (#patients=XX) (#episodes = XX)	Estimate (0.95 CI)	p-value	Estimate (0.95 CI)	p-value
EDTR Day 30	XX (XX%)	XX (XX%)	X.XX (X.XX to X.XX)	X.XXX	X.XX (X.XX to X.XX)	X.XXX
EDTR Day 90	XX (XX%)	XX (XX%)	X.XX (X.XX to X.XX)	X.XXX	X.XX (X.XX to X.XX)	X.XXX
Admission Day 30	XX (XX%)	XX (XX%)	X.XX (X.XX to X.XX)	X.XXX	X.XX (X.XX to X.XX)	X.XXX
Admission Day 90	XX (XX%)	XX (XX%)	X.XX (X.XX to X.XX)	X.XXX	X.XX (X.XX to X.XX)	X.XXX
Surgery Only						
	Number of Observed Events (%)		Odds Ratio		Absolute Difference	
Outcomes	Intervention (#patients = XX) (#episodes = XX)	Control (#patients=XX) (#episodes = XX)	Estimate (0.95 CI)	p-value	Estimate (0.95 CI)	p-value
EDTR Day 30	XX (XX%)	XX (XX%)	X.XX (X.XX to X.XX)	X.XXX	X.XX (X.XX to X.XX)	X.XXX
EDTR Day 90	XX (XX%)	XX (XX%)	X.XX (X.XX to X.XX)	X.XXX	X.XX (X.XX to X.XX)	X.XXX
Admission Day 30	XX (XX%)	XX (XX%)	X.XX (X.XX to X.XX)	X.XXX	X.XX (X.XX to X.XX)	X.XXX
Admission Day 90	XX (XX%)	XX (XX%)	X.XX (X.XX to X.XX)	X.XXX	X.XX (X.XX to X.XX)	X.XXX
Factors used for the adjustment: XXX, XXX, XXX, XXX						

5. Analysis for Aim 2b: Impact on initiation of adjuvant chemotherapy and chemotherapy duration.

5.1. Outcomes and summary measures

We do not have preliminary data to support a specific effect size. However, we expect that patients exposed to eSyM may be able to: 1) initiate adjuvant therapy sooner; and/or 2) remain on their chemotherapy regimens for longer duration. These time intervals are straightforward to measure from EHR encounter and date fields. The outcomes for Aim 2b and the projected minimum sample size are summarized in **Table 10**.

Table 10: Outcomes of Aim 2b					
Outcome	Type of outcome	Summary measure for each group	Summary measure for between-group difference	Cohort	Projected minimum sample size
Days from chemo regimen start date to stop date	Continuous	Mean*	Absolute Difference (AD)	All MO	504 patients/site; 3024 MO patients in total 1512 eSyM+ and 1512 eSyM-
Days from surgery date to start of adjuvant chemotherapy	Continuous	Mean*	AD	Surg who get adjuvant Rx (roughly 40% of all Surg)	202 patients/site; 1212 surg patients in total 606 eSyM+ and 606 eSyM-

* Because the maximum follow-up period of each episode is 1 year, the data will be truncated at 365 days when the mean value is calculated.

For MO patients, the outcome is time from the first dose to the last dose of a specific regimen. We will censor follow-up at 1 year. For Surg, the denominator population consists of patients who receive *any* adjuvant chemotherapy within 6 postoperative months. Tumor registry stage distribution at our 6 sites indicates that this will be 202 patients per site or 1212 in total.

The type of censoring involved in this analysis is only the truncation at the maximum follow-up period of 1 year. Thus, we will not employ censored time-to-event analysis methods but handle the outcomes as continuous outcomes.

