## 1.0 Schema

## 2.0 Background

**Deficits in management of common symptoms cause substantial morbidity for cancer patients.** In the United States, nearly 1.74 million people will be diagnosed with cancer in 2018. While there will be approximately 600,000 cancer deaths, better treatment has contributed to lower mortality rates. However, the morbidity toll of cancer treatment remains immense. Poor symptom control decreases quality of life, increases the need for emergency care, and even deters some patients from receiving effective therapy. For patients with cancer receiving chemotherapy, adverse symptoms add to distress. For surgical patients, poorly managed symptoms delay recovery and interfere with timely receipt of adjuvant treatments and the return to usual activity levels. Patients are reluctant to “complain” or perceive that symptoms are unavoidable. The raging US opioid epidemic has further complicated pain management for cancer patients.

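### The surgical Aim 2b comparison is restricted to patients who received adjuvant chemotherapy within six months, so the difference in days can mix a timing effect with a change in who is included

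*SAP*

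**What the plan says.** SAP 5.1 and Table 10 define the surgical outcome of Aim 2b as "Days from surgery date to start of adjuvant chemotherapy", summarised by a mean in each condition and an absolute difference. The analysis set is limited by a later event: "the denominator population consists of patients who receive *any* adjuvant chemotherapy within 6 postoperative months". Table 10 describes the cohort as "Surg who get adjuvant Rx (roughly 40% of all Surg" patients, with a projected size of "202 patients/site; 1212 surg patients in total", divided equally between the exposed and control conditions (606 each).

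The hypothesis in 5.1 is that exposed patients may "initiate adjuvant therapy sooner". On method, 5.1 says "we will not employ censored time-to-event analysis methods but handle the outcomes as continuous outcomes", on the ground that the only censoring is truncation at one year. SAP 5.2 then reports the mean difference with a 95% confidence interval and p-value.

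The rationale is in Protocol 2.0 Background: for surgical patients, "poorly managed symptoms delay recovery and interfere with timely receipt of adjuvant treatments". The same section says more generally that poor symptom control keeps some patients from effective treatment.

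Neither Table 5 nor Table 10 lists the proportion of surgical patients who start adjuvant chemotherapy. The June 2024 addendum moves the primary analysis to first episodes and to models without random effects, and leaves this denominator as it was.

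**The concern.** Under SAP 4.2, exposure is fixed at the trigger event. Starting adjuvant chemotherapy comes later. A comparison restricted to those who started is therefore made within a subset that exposure can alter, and randomising sites to steps does not protect it.

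Suppose better symptom control lets some patients start who otherwise would not have done so. They enter the exposed denominator, while their counterparts in the control periods are absent. If these added patients start later than average, they raise the exposed mean and hide a real gain in timing. If they start earlier than average, they lower it and overstate the gain. Either way, the reported number of days cannot be assigned to timing alone. At stake is the interpretation of one secondary result: Aim 2b could show no effect, or a small apparent delay, partly because more patients reached treatment.

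**Working it through.** **The plan's own figures.** Table 3 gives 504 surgical patients per site. 0.40 × 504 = 201.6, rounded up to 202; 202 × 6 = 1212; 1212 / 2 = 606. These match Table 10. The equal split implies the same uptake in both conditions.

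The detectable effects in Table 11B also reproduce with the Hussey–Hughes stepped-wedge variance: 6 sites, 7 periods, one site crossing per step, 1212 / 42 = 28.9 patients per site-period, two-sided 5% (stated for Aim 2a, assumed here) and 80% power.

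| ICC | Stated | Recomputed | Stated effect × conservative SD |
|---|---|---|---|
| 0.01% | 0.217 | 0.217 | 0.217 × 65 = 14.1 days |
| 1% | 0.256 | 0.255 | 0.256 × 55 = 14.1 days |
| 5% | 0.271 | 0.270 | 0.271 × 52 = 14.1 days |

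The power figures are sound for the set as defined. The issue is the definition of the set.

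**Effect of a change in composition.** Inputs from the SAP: control uptake 0.40 (Table 10) and control mean 56 days (5.3). Inputs assumed, because the documents give none of them: extra uptake *u*, mean start day *L* of the added patients, and gain *c* in days among those who would start anyway.

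Observed difference = [0.40 × (56 − c) + u × L] / (0.40 + u) − 56.

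With c = 5, the true timing effect in existing starters is −5 days:

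| u | L | Calculation | Observed difference |
|---|---|---|---|
| 0.03 | 90 | (20.4 + 2.7) / 0.43 − 56 | −2.3 |
| 0.03 | 100 | (20.4 + 3.0) / 0.43 − 56 | −1.6 |
| 0.03 | 120 | (20.4 + 3.6) / 0.43 − 56 | −0.2 |
| 0.05 | 90 | (20.4 + 4.5) / 0.45 − 56 | −0.7 |
| 0.05 | 100 | (20.4 + 5.0) / 0.45 − 56 | +0.4 |
| 0.05 | 120 | (20.4 + 6.0) / 0.45 − 56 | +2.7 |

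The gain shrinks in all six cases and the sign changes in two.

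The sign flips where 0.40 × c = u × (L − 56). For c = 5, that is total uptake of 0.40 + 2/34 = 45.9% at L = 90, and 0.40 + 2/64 = 43.1% at L = 120.

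**The other direction.** With u = 0.05 and L = 40, also assumed, the result is (20.4 + 2.0) / 0.45 − 56 = −6.2 days, so the benefit is overstated. With u = 0 and the same patients starting, the result is −5, undistorted.

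**Keeping non-starters.** Take restricted mean days without adjuvant chemotherapy to day 183 in all surgical patients, in the worst case above (u = 0.05, L = 120, c = 5):

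- Control: 0.40 × 56 + 0.60 × 183 = 132.2 days.
- Exposed: 0.40 × 51 + 0.05 × 120 + 0.55 × 183 = 127.05 days.
- Difference: −5.15 days, so the favourable sign is kept.

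**Precision of an all-patient proportion.** There are 504 × 6 = 3024 surgical patients, the same number as in Table 11A, so its standardised effects can be borrowed. The SD of a 40% proportion is √(0.40 × 0.60) = 0.490. Then 0.138, 0.170 and 0.174 times 0.490 give 6.8, 8.3 and 8.5 percentage points.

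**The case against.** The strongest reply is that the plan treats receipt as a matter of stage: 5.1 takes its 202 per site from the tumor registry stage distribution. If eSyM does not change who starts, the recipients-only difference is interpretable. The Background sentence on surgery concerns timeliness, and the sentence on patients kept from treatment is general. The extra uptake, start days and 5-day gain are all assumed, and four of the six scenarios show no reversal. This part of the reply stands. It limits how firmly the bias can be asserted, but does not remove it, because the plan contains no outcome that would show whether uptake changed.

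A reader might infer that the estimate can never be an effect of eSyM, or that it must reverse sign whenever eSyM works through uptake. The documents support neither. Reversal needs higher uptake, added patients who start late enough, and a gain in existing starters small enough to be outweighed. A reader might also take 7 days in Table 11B as a target that these shifts approach. It is a detectable difference at the lower SDs (26 to 32 days), and 5.3 leads with 14 days. Masking a benefit is more likely than a statistically significant false delay.

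Replacing the endpoint with yes/no tests at fixed days would go too far. Day 56 is only the assumed control mean, and power for modest changes in uptake would be low. That objection also stands, and the remedy should add to the existing outcome.

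**Conclusion.** The point holds in conditional form. The surgical Aim 2b contrast conditions on a post-exposure event that the Protocol gives reason to think symptom control could affect, and nothing in the SAP or addendum retains the non-starters. With 3 to 5 points of extra uptake, added starters at a mean of day 90 to 120 and a true 5-day gain, the observed difference is about −2.3 to +2.7 days. That range rests on the three assumed inputs; only the 40% and the 56 days come from the SAP. The bias could also favour eSyM. It is absent if eSyM does not change who starts. The consequence is confined to a secondary aim, and the change is worth making because it is cheap.

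**What to change.** In SAP 5.1 and Table 10, add the proportion starting adjuvant chemotherapy within six months of surgery, in all eligible surgical first episodes. A subset defined at baseline by stage, from the staging codes listed in Protocol 12.0, is an alternative. Use the Aim 2a logit model with G-computation for the absolute difference. Count patients who die before starting as non-starters, in line with SAP 4.4. Optionally add restricted mean days without adjuvant chemotherapy to six months, with non-starters retained.

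Keep the recipients-only mean difference, report it beside the proportion as supportive, and state that it is not to be read on its own as an effect of eSyM. Because the addendum shows that models had already been fitted, date the addition and label it as such.

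The cost is one more analysis from dates already collected. Patients with no indication for adjuvant therapy, including those without cancer, dilute the difference; the stage-defined subset would reduce this. Precision is limited to about 7 to 9 percentage points with 3024 patients, so the confidence interval should carry the interpretation, and a non-significant difference should not be read as unchanged uptake.

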**Defining and operationalizing the denominator:**

- To determine if a patient has a diagnosis of one of the priority cancer types, use ICD-10 diagnosis codes: 15.0-16.99 (esophago-gastric) C17.0-C21.9 (small int. colorectal) C22.0-24.9 (hepatobiliary) C23-C25.9 (pancreas), C34-34.9: lung, C53.0-53.9 (cervix) C54-54.9 (uterine) and/or C56-57.9 (ovarian). When it comes time to execute, this list may be modified. CPT and procedure codes as well as EPIC operating room scheduling lists will be used to determine if a patient is scheduled for a priority surgery.
- Participants assigned to eSyM+ may be trained to use eSyM by their local clinic/study staff. Surgical patients may be trained to use eSyM at the time of surgical discharge (or at the site's discretion patients may receive training in how to use eSyM at a preoperative visit). Med Onc patients may be trained to use eSyM at the time of their first chemotherapy dose visit or at the time of a pre-treatment visit for chemotherapy teaching (at the site's discretion). Epic reports may also be used to identify eligible patients who are assigned or will be assigned to eSyM so that training of the eligible patients can be done by study research staff via telephone or email before or after beginning treatment or having surgery.
- Participants in the eSyM- cohort will meet priority population criteria and be seen at a participating site between 1/1/2018 and the site's eSyM go-live date. Participants in the eSyM+ cohort will meet priority population criteria and be seen at a participating site after their eSyM go-live date through March 31, 2024.

**Mode of Participation:** Patients will have a *choice* of their preferred mode of eSyM participation and switching can be accommodated. Patients with a smart phone will be offered that approach first, however all patients will be notified that access to eSyM is available as long as they can access the secure patient portal (MyChart). eSyM can be accessed securely through the MyChart portal on any web-enabled device. Alternatives to smart phone reporting include

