Occurrence of 1 st chemotherapy discontinuation during one-year follow-up period	Time to event	Incidence Rate on (0, 365d)	IRD and IRR	All MO
Occurrence of 1 st admission during one-year follow-up period	Time to event	Incidence Rate on (0, 365d)	IRD and IRR	All MO
Occurrence of 1 st re-operation during one-year follow-up period	Time to event	Incidence Rate on (0, 365d)	IRD and IRR	All Surg
Occurrence of 1 st re-admission during one-year follow-up period	Time to event	Incidence Rate on (0, 365d)	IRD and IRR	All Surg
Death during one-year follow-up period	Time to event	Incidence Rate on (0, 365d)	IRD and IRR	MO and Surg
Composite of EDTR, Hospitalization, and Death event occurrence status at Day 30	Binary	Proportion	Absolute Difference (AD) and Odds Ratio (OR)	MO and Surg
Death during 30-day post-chemotherapy start date (for MO) or at 30-day post-surgical discharge date (for Surg)	Time to event	Incidence Rate on (0, 30d)	IRD and IRR	MO and Surg
Notes:				

 The Day 1 is defined the chemotherapy start date for MO and the discharge date for Surgery. All outcomes are defined in relation to the date of discharge from hospital (for Surg) or the initiation date of a new chemotherapy regimen (for MO). Note that events occurring on the first day of chemotherapy or the day of discharge after surgery will be excluded, because they could not have been impacted by the eSym program. 				

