- Death is a competing event for EDTR and Hospitalization. In the primary analyses for EDTR and Admission, those who die without EDTR or Hospitalization will not be excluded from the analyses but included in the denominator when calculating the EDTR rate and Admission rate. Caution should be exercised in interpreting the intervention effect on these non-fatal outcomes. Because those who die before these non-fatal events will never experience it, the intervention effect on these non-fatal events will be biased in favor of either the control or intervention group where more deaths are observed. Therefore, when assessing the effectiveness of the intervention, we will also consider its impact on reducing death (a secondary outcome; see Table 5).
- As a sensitivity analysis for concluding the effectiveness of the intervention, we will analyze the composite of EDTR, Hospitalization, or Death event occurrence status at Day 30 (a secondary outcome; see Table 5), which is not subject to the competing risk problems.

Handling of potentially differentiable follow-up duration across episodes:

- While the planned follow-up duration for each episode is one-year, the actual follow-up durations of some episodes will be shorter than one year due to the occurrence of another trigger event or lost-to-follow-up during the one-year follow-up. Thus, the follow-up duration will be different across the episodes.
- For binary outcomes (i.e., the event status yes/no), the length of follow-up time will not be considered in the analysis. We expect that this will not affect the analysis of the primary endpoint (EDTR at Day 30) because we expect that we will have at least 30 days of follow-up for all episodes. The potential reason of censoring of follow-up is the occurrence of another trigger event during the follow-up time. It is unlikely for a patient to have another trigger event within 30 days after the previous trigger event.
- For count data, we will take the length of the follow-up period for each episode into account. Specifically, we will use Poisson regression models, where the logarithm of follow-up duration of each episode will be included as offset in the models.

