4.6. Sensitivity analyses

Change in eSyM recall period:

During the study, there was a minor update to the eSyM symptom questionnaire. eSyM originally collected symptom information with a 7-day recall period, but a mid-study update altered this to a 24-hour recall period. Using eSyM+ data only, we will summarize frequencies of severe symptoms reported before the update and after the update. For the evaluation of eSyM intervention, we will not distinguish eSyM intervention before and after the update in the primary analysis. As sensitivity analyses, we will assess the impact of this update on each outcome.

- Sensitivity Analysis 1: We will run the same analysis as the primary analysis, excluding the eSyM+ episodes with a 7-day recall period.
- Sensitivity Analysis 2: We will modify the GLMM model used for the primary analysis. The intervention group variable will be a categorical variable with three levels – control, eSyM+ with 7-day recall, and eSyM+ with 24-hour recall. We will test if there is any difference between the 7-day and 24-hour recall.

Missing data:

Given the short 30-day interval for the Aim 2a primary endpoint and our pragmatic outcome, we expect the dropout fraction and missing data at Day 30 to be negligible. Subjects with no hospital encounters by Day 30 will be included in the analysis as having had no EDTR.

Regarding missing covariates, the primary analysis will be based on the following data handling.

- 1) Race/Ethnicity: Subjects with missing race/ethnicity are categorized as “Other/Unknown” and included in the analysis.
- 2) Employment: Subjects with missing employment information are categorized as “Other/Unknown” and included in the analysis.
- 3) Insurance type: Subjects with missing insurance type are categorized as “Other/Unknown” and included in the analysis.
- 4) Rurality: Subjects with missing rurality will be excluded from the analysis.
- 5) Socio-economic status: Subjects with missing socio-economic status are classified as “poverty level 2” and included in the analysis.

Note that the preliminary data check found that the other covariates do not have missing values.

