5.2. Data Analysis

Similar analyses to those for Aim 2a (see Section 4) will be performed. GLMMs will be used with the indemnity link function for these continuous variables. The intervention effect will be summarized as the mean difference between eSyM+ and eSyM- and reported with a corresponding 95% confidence interval and p-value.

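### Aim 2b analyses chemotherapy duration without censoring on the premise that only the 1-year cap applies; SAP 4.4 contradicts that premise and no rule covers regimens still open when observation ends

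*SAP*

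**What the plan says.** For medical oncology (MO), SAP 5.1 defines the measure: "For MO patients, the outcome is time from the first dose to the last dose of a specific regimen". Durations are capped at 365 days. The section then states that "The type of censoring involved in this analysis is only the truncation at the maximum follow-up period of 1 year" and concludes from this that "we will not employ censored time-to-event analysis methods but handle the outcomes as continuous outcomes". SAP 5.2 fits an identity-link model similar to that of Section 4 and reports a mean difference in days. It adds no rule for durations that are only partly observed.

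SAP 4.4, on unequal follow-up, says that "the actual follow-up durations of some episodes will be shorter than one year due to the occurrence of another trigger event or lost-to-follow-up". For count outcomes it corrects for this with a follow-up offset. For time-to-event outcomes it uses an event/censoring indicator with exposure time as the offset. SAP Table 5 lists, among the time-to-event outcomes for all MO, first "chemotherapy discontinuation during one-year follow-up period".

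The missing-data reassurance in SAP 4.6, "we expect the dropout fraction and missing data at Day 30 to be negligible", concerns the Aim 2a primary endpoint only. The June 2024 addendum moves the primary analysis to first episodes and a generalized linear model, and leaves Aim 2b censoring untouched.

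**The concern.** Section 5.1 gives one reason for doing without censored-data methods, and section 4.4 contradicts it. A patient lost at month 3 while still on treatment is censored in the Table 5 discontinuation analysis. In Aim 2b the same patient has a last observed dose at month 3 and, if the text is followed literally, a complete three-month duration.

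A second trigger has a similar effect. SAP 4.2 assigns data after the second trigger to the new episode. A new treatment plan will often be a true end of the regimen, but a qualifying surgery need not be, so an open regimen can be closed by a data rule.

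At stake is the accuracy of the Aim 2b mean difference. Cut durations pull arm means down. The between-condition difference is attenuated if loss is equal and can move either way if it is not.

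**Working it through.** **1. Reproduce the plan's figure (SAP Table 11A).** Inputs: 3,024 MO patients, 6 sites, 7 periods, 72 per site-period (12 per month × 6 months, SAP 3.3), one site crossing per step, 80% power. The two-sided 5% level is stated for Aim 2a and assumed to carry over.

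The Hussey-Hughes variance, with total variance 1, s² = (1 − ICC)/72 and t² = ICC, is

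Var = I·s²(s² + T·t²) / [(I·U − W)s² + (U² + I·T·U − T·W − I·V)t²], where I = 6, T = 7, U = 21, W = 91, V = 91.

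Detectable effect = (1.960 + 0.842)·√Var:

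| ICC | √Var | Computed | Stated |
|---|---|---|---|
| 0.01% | 0.0493 | 0.138 | 0.138 |
| 1% | 0.0606 | 0.170 | 0.170 |
| 5% | 0.0621 | 0.174 | 0.174 |

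The table reproduces. It makes no allowance for durations cut before one year. In the 28-day rows the standard error is about 10 days (for example 202 × 0.0493 = 9.96).

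**2. Shift in one arm's mean.** Assume exponential durations with 365-day capped mean (1 − e^(−365r))/r.
- A mean of 180 days (the control value in SAP 5.3) gives r = 0.004468. A mean of 208 days (180 + 28) gives r = 0.003436.
- If a patient is cut at a time uniform on 0 to 365, the mean observed duration in the 180-day arm is 113.4 days, a shortfall of 180 − 113.4 = 66.6 days.
- Each 5% of the arm cut this way costs 0.05 × 66.6 = 3.3 days; 10% costs 6.7 and 20% costs 13.3.

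These are shifts in a single arm. They should not be set directly against the 14- to 28-day between-group differences in Table 11A.

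**3. Effect on the difference.** Let f be the probability of loss by day 365 if treatment continued, with exponential loss rate g = −ln(1 − f)/365. The recorded mean is then (1 − e^(−365(r+g)))/(r + g). Power is Φ(difference/SE − 1.96), with SE held at its planned value. The documents give no 1-year loss rate, so every f is an assumption. The true difference is 28 days.

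| Loss, control / eSyM+ | Control mean | eSyM+ mean | Difference | Power |
|---|---|---|---|---|
| 0 / 0 | 180.0 | 208.0 | 28.0 | 80% |
| 5% / 5% | 176.6 | 203.8 | 27.2 | 78% |
| 10% / 10% | 173.2 | 199.5 | 26.3 | 75% |
| 20% / 20% | 166.0 | 190.7 | 24.6 | 69% |
| 10% / 20% | 173.2 | 190.7 | 17.5 | 42% |
| 20% / 10% | 166.0 | 199.5 | 33.5 | 92% |

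With no true effect, 10% / 20% gives a false difference of 166.04 − 173.19 = −7.15 days. The reverse imbalance gives +7.15.

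**The case against.** **No scoring rule is stated.** The SAP nowhere says that lost patients count as stopped. Table 10 uses regimen start and stop dates, and the protocol collects a treatment-plan end date, so a patient without a stop date might be excluded instead. This stands: the exact criticism is that the rule is missing. Exclusion would not be harmless, because longer regimens are more likely to be cut.

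**Loss may be small.** SAP 4.4 names another trigger as the potential reason for censoring, and in MO a new plan is often a genuine regimen end. But that remark supports the Day 30 endpoint, the same section also names loss to follow-up, and Aim 2b needs 365 days.

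**Table 5 already gives a censoring-aware result.** True for a closely related outcome. It yields a rate ratio and rate difference, and does not correct the mean in days.

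**A stronger reading to resist.** A reader might infer that the data cut shortens only eSyM+ durations and so hides a benefit. The protocol includes eSyM+ patients "seen at a participating site after their eSyM go-live date through March 31, 2024" and estimates completion of secondary analyses by August 31, 2024. Treat that date as the data cut and take 12 MO patients per month per site. Then about 501 of 2,725 eSyM+ MO patients (18%) lack a full year, by an average of about 29 days of recorded duration: 0.184 × 29.2 = 5.4 days off the crude eSyM+ mean. The documents do not support this as the bias of the planned estimate:
- Those patients start from about September 2023. Every site's MO version was live by April 18, 2022 (SAP 3.6), so there are no concurrent controls, and site and calendar-time adjustment largely reassigns the drop to time. Fitting the planned adjustment to the expected values gives 0.0 days with categorical periods. With splines it gives −0.3 or −1.4 days (three interior knots) and +5.5 or +3.4 days (three knots in total), depending on when controls begin.
- SAP 3.6 ends accrual in February 2023. On that date every episode reaches one year by the end of February 2024, and the shortfall under the same assumed data cut is zero.
- No data cut is stated, and the protocol says its dates may change.

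**Conclusion.** The point holds in limited form. The reason given in SAP 5.1 for an uncensored analysis conflicts with SAP 4.4, and neither section 5.2, the Day 30 statements nor the addendum repairs it. Taken literally, the plan enters unfinished regimens as finished ones.

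On the assumptions above (exponential durations, non-informative loss, fixed SE), equal loss of 5% to 20% costs about 1 to 3 of 28 days and 2 to 11 points of power. Unequal loss can do more, in either direction. The actual size and direction are unknown, because no 1-year loss rate is given and nothing in the documents says that loss differs by condition. A claim that the plan would conceal a longer duration under eSyM goes beyond the evidence. The Aim 2a primary outcome at Day 30 is unaffected. This should be corrected, but it does not threaten the trial's main conclusion.

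**What to change.** In SAP 5.1:
- Delete the premise that the 1-year cap is the only censoring.
- Define end of observation for each episode as the earliest of 365 days, loss to follow-up, data cut-off, or a second trigger that does not end the regimen.
- Treat patients still on regimen at that point as censored, and count regimen change and death as stops.
- Estimate the 365-day restricted mean difference. Kaplan-Meier pseudo-observations in the same identity-link model would do this, as would another censoring-aware restricted-mean method.
- Report the number and timing of censored durations by condition.

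The effect remains a mean difference in days capped at 365. The cost is SAP wording, a little more programming and slightly wider intervals, with no new data collection. If loss proves trivial, the result will barely change.
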